6.8 Study-specific Procedures

6.8.1 Electrocardiogram

A 5- or 12-lead ECG will acquire QTc prior to study drug administration screening, 30 and 96 hours after study drug administration.

Refer to MOP for details.

6.8.2 Pupillometry, Dark-Adapted

Dark-adapted pupillometry will measure pupil diameter using a goggle-based, camera-like device (I-Portal® Falcon, <https://www.neurolign.com/products/#hardware>). A goggle-based system effectively allows the participant to be in the dark while room lights are on for research staff. The participant will wear the goggles continuously for the first hour of PK sampling. Thereafter, the goggles can be removed. See **Table 5** for details when this measurement should be completed.

Refer to MOP for details.

6.8.3 Vital Signs

Vital signs collected at screening include: RR, HR, BP, and SpO₂. Vital signs collected at 30,48,72 and 96 hours include RR, CO₂, HR, BP, SpO₂. Respiratory rate and end-expired CO₂ concentration are recorded using Medtronic Capnostream monitor with FilterLine sampling lines (<https://www.medtronic.com/covidien/en-us/products/capnography/capnostream-20p-bedside-patient-monitor.html> (<https://www.medtronic.com/covidien/en-us/products/capnography/filterline-etc02-sampling-lines.html>)).

Refer to MOP for details.

6.8.4 Observed Sedation, MOAA/S

Sedation will be observed and recorded by the study team using the Modified Observer's Assessment of Alertness/Sedation (MOAA/S).

Modified Observer's Assessment of Alertness/Sedation [MOAA/S]	
Responsiveness	Score
Responds readily to name spoken in normal tone	5 (alert)
Lethargic response to name spoken in normal tone	4
Responds only after name is called loudly and/ or repeatedly	3
Responds only after mild prodding or shaking	2
Responds only after painful trapezius squeeze	1
Does not respond to painful trapezius squeeze	0

Refer to MOP for details.

6.8.5 Thermal Pain Tolerance Threshold

Thermal pain tolerance will be measured by a 3 cm² computer-controlled Peltier-type thermal stimulator (Pathway; Medoc Advanced Medical Systems, <https://medoc-web.com/products/pathway-model-ats/> or similar thermal stimulator). The stimulator delivers painful heat stimuli to the volar side of the forearm. Before any stimulus is applied, participants are familiarized with the test procedure and instructed on how to evaluate their pain. Pain is evaluated using a standard verbal scale from 0 (no pain) to 100 (worst possible pain).

The thermode system's baseline temperature is set at 32°C. The computer-controlled thermode system is programmed to gradually increase the stimulus (0.8°C/sec) until participants press a stop button, which indicates maximum tolerable temperature was reached and initiates immediate thermode cooling. The maximum tolerable temperature is recorded.

The thermode system's maximum temperature is set to 52°C to prevent thermal injury. If the thermode reaches 52°C without the participant pressing the button, then temperature increase ceases and immediate thermode cooling is initiated, and 52°C is recorded as the maximum tolerable temperature.

The maximum temperature testing is repeated three times for each time event, as the probe is moved and cooled between each stimuli, the averages of the three maximum temperatures and pain ratings are recorded,. The primary outcome measure is the average maximum tolerable temperature.

Refer to MOP for details.

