3 OBJECTIVES AND OUTCOME MEASURES

	Objective	Measures	Endpoints
Primary	Characterize the PK of methadone hydrochloride injection	Plasma concentrations	1. Clearance (CL) 2. Volume of distribution (Vz) 3. Half-life (t _{1/2}) 4. Area under the curve (AUC) 5. Maximum concentration (C _{max}) 6. Time to maximum concentration (T _{max}) 7. Minimum concentration (C _{min}) 8. Elimination rate constant (k _e)
Secondary	Characterize the PD effect of methadone hydrochloride injection	1. Dark-adapted pupillometry 2. Observed sedation 3. Thermal pain tolerance thresholds 4. Subjective self-assessment of methadone effects using visual analog scale (VAS)	Change in pupillometry, observed sedation, thermal pain tolerance thresholds, and VAS from pre-dose to each post-dose time point
Secondary	Characterize the tolerability of methadone hydrochloride injection	1. Adverse events (AEs) 2. Serious adverse events (SAEs) 3. Suspected Unexpected Serious Adverse Reactions (SUSARs) 4. Safety events of special interest (QTc)	For AEs, SAEs, SUSARs: Proportion of participants from baseline to the end of safety follow-up For SESI: Change in QTc from baseline to the end of safety follow-up
Exploratory	Characterize exposure-response relationships	Plasma concentrations and VAS	Correlation of plasma concentrations to VAS score at each post-dose VAS time point

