11.3 Analysis Plan

Noncompartmental analysis will be conducted to determine methadone PK. Compartmental modeling may be explored. Additional details are in the statistical analysis plan.

Descriptive statistics, such as number of observations, mean, median, standard deviation, standard error, minimum, and maximum, will be presented for continuous variables (such as age, weight, etc.). Other descriptive statistics, such as counts, proportions, and/or percentages, will be presented to summarize discrete variables (such as race, sex, etc.). All descriptive analyses will be presented overall. A 95% confidence level will be used for confidence intervals. A detailed description of statistical methods and secondary analyses will be prepared and presented in the statistical analysis plan prior to data lock for final analyses.

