11.3.2 Secondary Analysis

1) The relationship between methadone concentrations/other PK parameters and endpoints of change in pupillometry, observed sedation levels, thermal pain tolerance thresholds, change in VAS from pre to post dose, and change in respiratory rate will be evaluated using standard descriptive statistics. Descriptive summaries of the endpoints predose, postdose, end of follow-up will be presented. The change between time points also will be presented, along with the 95% CI, t-test, and p-value.

2) The following endpoints will be analyzed in the safety analyses:

Incidence of safety related events

- A. AE related to study procedure
- B. SAE related to study procedure
- C. SUSAR related to study drug
- D. Safety Events of Special Interest (QTc prolongation)

In addition, changes in QTc interval will be assessed over time.

All AEs recorded during the study period will be coded with Medical Dictionary for Regulatory Activities (MedDRA) Version March 2018. Summaries of AE will be tabulated for the following types:

- A. Number (%) of participants with any AE
- B. Number (%) of participants with any SAE
- C. Number (%) of participants withdrawn from treatment due to SUSAR

All summaries will be reported in total and by study site.

Additional analyses (e.g., Exposure-Response [safety] analysis) and summaries may be derived if deemed appropriate and will be further described in the SAP.

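### Thermal readings stopped at 52°C are right-censored but averaged as observed values, so if the cap is reached the mean change is biased toward zero and its 95% CI under-covers

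*Combined protocol and SAP*

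**What the plan says.** Section 6.8.5 describes a thermode that starts at 32°C and is "programmed to gradually increase the stimulus (0.8°C/sec) until participants press a stop button". Its "maximum temperature is set to 52°C to prevent thermal injury". When that limit is reached without a button press, "52°C is recorded as the maximum tolerable temperature". The test is done three times per time point and "the averages of the three maximum temperatures and pain ratings are recorded". The section then adds: "The primary outcome measure is the average maximum tolerable temperature". This means the main measure within the thermal test, because the trial's primary endpoints are pharmacokinetic.

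Section 3 makes the thermal measure part of a secondary endpoint: "Change in pupillometry, observed sedation, thermal pain tolerance thresholds, and VAS from pre-dose to each post-dose time point". Section 11.3.2 sets the analysis: "The change between time points also will be presented, along with the 95% CI, t-test, and p-value". The same section relates methadone concentrations to thermal tolerance. Section 11.3 states: "A 95% confidence level will be used for confidence intervals".

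No section of the document treats 52°C as a limit of observation, asks for the number of capped ramps, or names a censored-data method. Section 11.3 defers detailed methods to a statistical analysis plan and Section 6.8.5 defers detail to a manual of procedures. The document contains neither text beyond the protocol's own statistical section.

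**The concern.** A participant who lets the ramp run to 52°C has a tolerance of 52°C or more, and the plan enters 52 as if it were the tolerance itself. A drug that raises tolerance makes capping more frequent after dosing than before, so the cap removes more from the post-dose mean than from the baseline mean. The loss would be largest when the effect is largest and in participants whose baseline tolerance is already high.

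Two results are at stake. One is the estimated change in tolerance with its CI, at each of the 14 post-dose thermal times in Table 5. The other is the relation between concentration and effect, where a ceiling in the measurement can look like a true maximum drug effect. Section 2.2 gives the PK/PD relationship as the scientific reason for the study.

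There is also a recording problem. An average of 51.3°C could come from 52, 52 and 49.9 (sum 153.9, divided by 3) or from three uncapped readings. If only averages are kept, no later analysis can tell these apart.

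**Working it through.** The documents give no baseline tolerance, SD, effect size or expected share at the cap, so there is no planned figure to reproduce for this endpoint.

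**Inputs from the documents.** Cap 52°C; start 32°C; 0.8°C per second, so the cap is reached after (52 − 32)/0.8 = 25 s; mean of three ramps; about 20 participants (Section 5.1); 95% CI and t-test on change, taken as paired and two-sided at 0.05.

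**Assumed inputs (not in the documents).** Normal tolerance; baseline mean 46 to 50°C; between-person SD 1.5 or 2.5°C; mean rise d of 1 or 2°C with SD d/2; occasion SD 0.7°C; ramp SD 0.7°C.

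**Direction.** Let Y0 and Y1 be true ramp tolerance before and after dosing. The recorded value is min(Y, 52) = Y − (Y − 52)⁺, so

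bias of the mean change = E(Y0 − 52)⁺ − E(Y1 − 52)⁺.

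Averaging three ramps does not alter this expectation. The bias is negative whenever the mean excess above 52°C is larger after dosing than before, and zero if no ramp reaches the cap.

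**Size.** For a normal Y with mean m and total SD s, and z = (m − 52)/s, E(Y − 52)⁺ = (m − 52)Φ(z) + sφ(z).

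Worked case, baseline 50, SD 1.5, rise 2:
- Pre-dose s = √(1.5² + 0.7² + 0.7²) = 1.797, giving mean excess 0.120.
- Post-dose s = √(1.5² + 1² + 0.7² + 0.7²) = 2.057 with mean 52, giving mean excess 0.821.
- Bias = 0.120 − 0.821 = −0.70, so the capped mean change is 1.30 against a true 2.00, or −35%.

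The same calculation over other inputs is below. Coverage of the 95% CI comes from simulating the planned analysis (n = 20, 20,000 replicates), which gave the same mean changes to within rounding.

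| Baseline mean | SD | True rise | Post-dose ramps capped | Capped mean change | Relative bias | CI coverage |
|---|---|---|---|---|---|---|
| 46 | 1.5 | 1 | 0.4% | 1.00 | about 0% | 95% |
| 46 | 2.5 | 2 | 8% | 1.91 | −5% | 94% |
| 48 | 2.5 | 1 | 14% | 0.89 | −11% | 93% |
| 48 | 2.5 | 2 | 24% | 1.67 | −17% | 82% |
| 50 | 1.5 | 1 | 30% | 0.77 | −23% | 84% |
| 50 | 1.5 | 2 | 50% | 1.30 | −35% | 33% |
| 50 | 2.5 | 2 | 50% | 1.21 | −39% | 29% |

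**The test.** With no change in anyone, the simulated rejection rate stayed between 4.7% and 5.2% with the cap on. Power at a rise of 1°C moved from 92.5% to 90.0% (baseline 48, SD 2.5) and from 92.6% to 86.9% (baseline 50, SD 1.5). With light capping the t statistic can even rise, because the SD shrinks too: at baseline 46, SD 1.5, rise 3, mean t went from 7.41 to 7.59 while the mean change fell from 3.00 to 2.89.

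**Can it be recovered?** A censored-normal mixed model was fitted to individual capped ramps in 60 simulated trials per setting. Capped mean change against model estimate was:
- 0.94 and 1.03 (baseline 48, SD 2.5, rise 1)
- 0.73 and 0.98 (50, 1.5, 1)
- 1.31 and 2.00 (50, 1.5, 2)
- 1.16 and 1.89 (50, 2.5, 2)

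The data were generated from the same normal form that the model assumes, so this is a favourable setting for it.

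**The case against.** The strongest reply is that nothing in the documents shows the cap will be reached. With a baseline mean of 46°C the attenuation is 5% or less over the assumed range. That stands, and it is why the point is conditional.

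Three stronger readings are tempting and not supported:
- **That thermal tolerance is the only measure of analgesia.** Section 6.8.5 also collects a 0 to 100 verbal pain rating at each test, which can still fall when the temperature is capped. Section 4.6.2 lists VAS and self-reports under analgesia as well. However, none of the six VAS items in Section 6.8.6 asks about pain, and Section 3 does not name the verbal rating as an endpoint.
- **That the bias always runs toward less analgesia.** Capping shrinks change toward zero. If tolerance falls from a capped baseline, the cap hides the fall.
- **That the t-test is invalid.** Its level holds when there is no change. The damage is to the estimate and its CI.

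Two further points stand in part. Individual ramp values may already be kept, since Section 6.8.5 mentions recording the maximum tolerable temperature before it mentions averages, and the deferred SAP or manual might deal with the cap. Replacing the t-test outright with a censored model in about 20 people would lean on normality in a tail nobody observed, so the model belongs beside the planned summary. Neither point removes the need to say which values are stored and how capped ones are treated.

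**Conclusion.** The point holds as a conditional one. The recording rule turns a right-censored reading into an observed value, and the analysis described does not allow for it. If ramps reach 52°C, mean change is biased toward zero and its 95% CI covers less than 95%. Under the assumed inputs the attenuation runs from about 0% to 35% (SD 1.5) or 39% (SD 2.5), at baseline 50°C and a rise of 2°C. Coverage there falls to about 30%. These sizes rest wholly on assumed distributions, and the true share of capped ramps is unknown.

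The consequence is modest: one secondary pharmacodynamic endpoint in an open-label, single-arm study. The primary PK endpoints and the sample size, which rests on clearance, are unaffected. A reader should not infer that analgesia will be understated. That depends on the cap being reached more often, or by more, after dosing.

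**What to change.** 1. **Recording.** Store each of the three ramp temperatures with a flag for reaching 52°C without a button press, as well as the average. This has to be settled before data are collected.
2. **Reporting.** Give the share of capped ramps at baseline and at each post-dose time. Where capping is present, state that the capped mean change is a lower bound on any rise in tolerance.
3. **Analysis.** Pre-specify a censored-data (Tobit-type) mixed model on the individual ramps, presented alongside the planned capped summary, CI and t-test. Use the same treatment of capped values when relating concentration to thermal tolerance.
4. **Limit.** Section 2.4 describes a lockout of stimulus parameters above 53°C, while Section 6.8.5 sets the maximum at 52°C. These may be two separate safeguards, but the text does not say so. The passages must be reconciled, because a censored analysis needs an exact censoring point.

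The cost is one eCRF flag, three stored values per time point, and one extra model whose result depends on a distributional assumption. If few ramps are capped, the report will show it and the planned summary can be read as it stands.

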6.8.6 Subjective Self-assessment

Each participant will use a VAS to indicate levels of alertness/sedation (almost asleep to wide awake), energy level (no energy to full of energy), confusion (confused to clear headed), clumsiness (extremely clumsy to well-coordinated), anxiety (calm/relaxed to extremely nervous), and nausea (no nausea to worst nausea), each on a score of 0 to 100. Alternatively, plastic sliders may be used (<http://www.custompromotionalrulers.com/visual-analog-scale-vas-rulers/vas-pain-scale-rulers-0-10-cm-w/buckle-slider/> or similar), which are then scored from 0 to 100.

1. Please rate how awake you feel: 0 (asleep) - 100 (wide awake)

2. Please rate your level of energy: 0 (no energy) - 100 (full of energy)
3. Please rate how confused you feel: 0 (clear headed) - 100 (extremely confused)
4. Please rate how clumsy you feel: 0 (well-coordinated) - 100 (extremely clumsy)
5. Please rate how anxious you feel: 0 (totally relaxed) - 100 (extremely nervous)
6. Please rate if you feel nauseated: 0 (no nausea) - 100 (worst nausea)

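### Does the reversed anchor order for confusion and clumsiness in Section 6.8.6 leave the direction of two VAS items open?

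*Combined protocol and SAP*

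**What the plan says.** Section 6.8.6 (Subjective Self-assessment) has three parts.

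- **A descriptive paragraph** naming the two extremes of each scale. Two items read "alertness/sedation (almost asleep to wide awake), energy level (no energy to full of energy", two read "confusion (confused to clear headed), clumsiness (extremely clumsy to well-coordinated", and the last two read "anxiety (calm/relaxed to extremely nervous), and nausea (no nausea to worst nausea), each on a score of 0 to 100".
- **A sentence on plastic sliders** as an alternative, "which are then scored from 0 to 100".
- **Six numbered questions** with explicit scores. Item 3 is "Please rate how confused you feel: 0 (clear headed) - 100 (extremely confused" and item 4 is "Please rate how clumsy you feel: 0 (well-coordinated) - 100 (extremely clumsy".

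The scores feed two endpoints in Section 3. The secondary pharmacodynamic endpoint is "Change in pupillometry, observed sedation, thermal pain tolerance thresholds, and VAS from pre-dose to each post-dose time point". The exploratory endpoint is "Correlation of plasma concentrations to VAS score at each post-dose VAS time point". Section 11.3.2 adds that changes will be shown with a 95% confidence interval, a t-test and a p-value.

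**The concern.** For alertness, energy, anxiety and nausea, the end that the paragraph names first is the 0 end of the matching question. A reader who picks up that pattern and applies it to confusion and clumsiness would put 0 at the impaired end, which is the opposite of questions 3 and 4. The paragraph also looks coherent by itself: its first four items all run from impaired to unimpaired, as if two versions of the instrument had been left side by side.

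If scores recorded in one direction were read in the other, more confusion or clumsiness after methadone would appear as improvement, and the correlation with concentration would change sign. The size of the change, the width of the interval and the two-sided p-value would not move, so the planned t-test would not reveal the error.

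**Working it through.** **Step 1. Compare the two descriptions in Section 6.8.6.**

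| Item | End named first in the paragraph | 0 end in the numbered question | Same direction? |
|---|---|---|---|
| 1 Alertness | sleepy | sleepy | yes |
| 2 Energy | none | none | yes |
| 3 Confusion | confused | clear headed | no |
| 4 Clumsiness | clumsy | coordinated | no |
| 5 Anxiety | relaxed | relaxed | yes |
| 6 Nausea | none | none | yes |

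Two of six are reversed. Small wording differences elsewhere, such as how sleepy the low end of alertness is, do not affect direction.

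**Step 2. Ask which description is a scoring key.** The paragraph names two extremes per scale and says each is scored from 0 to 100. It never says that the first-named end is 0; that is inferred from word order. The numbered questions do say which end is 0 and which is 100. Their stems point the same way: asked how confused one feels, a higher rating naturally means more confused.

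**Step 3. Work out what a reversal does.** If a score x is replaced by 100 − x in every record:

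- change: (100 − post) − (100 − pre) = −(post − pre)
- the mean change reverses sign and its SD is unchanged
- a confidence interval [L, U] becomes [−U, −L], with the same width
- t becomes −t, with the same two-sided p-value
- a correlation r becomes −r

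Illustration with assumed scores: a rise from 5 to 35 on the numbered key is 35 − 5 = +30. On the opposite key it is 65 − 95 = −30.

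**Step 4. Find when the reported conclusion is wrong.**

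| Scores collected on | Scores interpreted on | Illustration reported as | Conclusion |
|---|---|---|---|
| numbered key | numbered key | +30 towards confused | correct |
| paragraph order | paragraph order | −30, away from clear headed | correct |
| paragraph order | numbered key | −30 read as less confused | wrong |
| numbered key | paragraph order | +30 read as more clear headed | wrong |

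Using the paragraph's order is therefore not enough to cause harm. If forms, coding and output labels all follow it, worsening is still reported as worsening. The error needs a mismatch between collection and interpretation.

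**Step 5. Bound the exposure.** Table 5 schedules the VAS at baseline and at 17 post-dose times (0:04, 0:10, 0:40, 1:00, 1:30, 2:00, 3:00, 4:00, 6:00, 8:00, 10:00, 12:00, 24:00, 30:00, 48:00, 72:00, 96:00), 18 in all.

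- Ratings per participant: 18 × 6 = 108, of which 18 × 2 = 36 belong to the two items. For 20 participants this is 2160 and 720.
- Mean changes, if every item is analysed separately at every post-dose time: 17 × 6 = 102, of which 17 × 2 = 34.
- Correlations, if also limited to the 12 VAS times that share a nominal time with a Table 4 sample (0:10, 1:00, 1:30, 2:00, 4:00, 6:00, 12:00, 24:00, 30:00, 48:00, 72:00, 96:00): 12 × 6 = 72, of which 12 × 2 = 24.

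The last two lines are ceilings under a full mismatch. They also assume analysis item by item, which Sections 3, 11.1.3 and 11.3.2 do not state: the endpoints refer only to the VAS or the VAS score, and the descriptive summaries in 11.3.2 are described as pre-dose, post-dose and end of follow-up.

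**The case for a change.** The strongest case for a change is that nothing else in the supplied documents repeats the direction. Sections 6.8.1 to 6.8.5 each refer the reader to the manual of procedures; Section 6.8.6 does not. The slider sentence comes straight after the paragraph and before the numbered questions, and it does not say which end is 0. If sliders were read one way and paper scales the other, changes would partly cancel: with a fraction f of participants reversed and the same average true change D in both groups, the observed mean is (1 − f)D − fD = (1 − 2f)D. That would shrink the estimate as well as threaten its sign. Rewording would cost almost nothing.

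Part of this stands. The two descriptions do disagree, and the planned test would not expose a full reversal. But the sliders are offered as another way of answering the same 0-to-100 items, and the questions that follow supply the anchors for those items. A mixture of keys would require staff to set aside the only explicit anchors on the page for some records. The study has a single site (Protocol Synopsis), and Section 16.1 derives the data collection forms from the electronic case report form, so one key throughout is the likely practice. If a reversal did occur and the key used for each record were known, 100 minus the score would restore it exactly. Pre-dose ratings would give a quick check, since healthy volunteers should mostly report little confusion or clumsiness before dosing; that is at most 2 × 20 = 40 ratings.

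**Conclusion.** The inconsistency is genuine but clerical, and no change to the plan follows. A team that follows Section 6.8.6 as written has one explicit key, in the questions themselves, and gets the right direction for both items. Putting the paragraph's two phrases in the other order would be tidier but would alter no score, estimate, interval or p-value. Confirming that forms, sliders and output labels share the numbered key is ordinary data-management checking before data lock.

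The affected material is two of six items within one of four secondary pharmacodynamic measures, plus the same two items in an exploratory correlation. The primary pharmacokinetic endpoints, the sample-size statement in Section 11.6 and the halting rules in Section 9.2 are untouched.

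This rests on two assumptions: that the numbered questions are what participants are asked, as their wording indicates, and that one key is used from collection through to reporting. The manual of procedures and the forms are not among the documents, and the conclusion does not depend on what they say about the paragraph. It would need another look only if they showed scores collected in one direction and labelled in the other.
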